Title: Influence of the Sleep Pattern in Patients Submitted to Bariatric Surgery

NCT number: 03485352

Date: 03/04/2021

Study protocol Participants and ethics

This longitudinal and observational study was performed with patients eligible for bariatric surgery in a private clinic in Uberlandia, Minas Gerais, Brazil, between June 2017 and April 2018. The inclusion criteria were patients in the preoperative period of bariatric surgery aged between 18 and 59 years, body mass index (BMI) $\geq 35 \text{ kg/m}^2$ associated with two comorbidities or BMI $> 40 \text{ kg/m}^2$ independent of comorbidities, and who would undergo Roux-en-Y gastric bypass or sleeve gastrectomy.

The exclusion criteria were patients who would undergo revisional surgery. The study was approved by the Human Research Ethics Committee (66023717.8.0000.5152), and all volunteers signed an informed consent form. The sample size required was determined using the G*Power software version 3.1.

The sample size calculations were based on f test linear ANOVA, with effect size of 0.15, an alpha level of 0.05, 95% power, repeated measures, within between interactions. Given these specifications, a total sample of 116 patients was required.

Follow-up evaluations

An initial questionnaire including socio-demographic and general information was applied in the preoperative period. Sleep and anthropometric pattern and food consumption were evaluated at the baseline, third and sixth months after surgery. Biochemical parameters were assessed at baseline and in the sixth month.

Sleep patterns and SJL The sleep pattern was determined by applying a questionnaire with questions: "What time do you usually go to sleep during the week?"; "How long (min) do you stay up in bed before sleep onset (after turning off the lights) during the week?"; "What time do you usually wake up during the week?"; "What time do you usually go to sleep on weekends?"; "How long (min) do you stay up in bed before sleep onset (after turning off the lights) on weekends?"; "What time do you usually wake up on weekends?". The bedtime on weekdays and at weekends was obtained whereas the time taken to fall asleep. SJL was calculated by the absolute difference between the mid-sleep time on work-free days and the mid-sleep time on work-days.

Anthropometric variables

The weight, height, waist circumference, hip circumference and neck circumference were measured by standardized methods at all evaluation appointments. The BMI was calculated and classified according to the recommended age ranges for adults (20 years $<$ age $<$ 60 years). Standardized cutoffs were used for waist circumference and neck circumference.

Metabolic profile

Serum levels of fasting glycaemia, fasting insulin, total cholesterol (TC), high density lipoprotein (HDL), low density lipoprotein (LDL), very low density lipoprotein (VLDL) and triglycerides (TG) were assessed to evaluate the metabolic profile. The blood samples were collected after a 12-h fasting period. All analyses were performed according to validated methodologies.

Dietary Intake Data

The food consumption was evaluated by two 24-h recalls (24HR) at each evaluation moment (baseline, third and sixth month), with one occurring on a weekday (applied in a private room with the interviewer and participant only) and the other one on the weekend (applied by phone, as done in previous studies) . Both 24HRs were conducted by a trained nutritionist using the multiple-pass method. Energy, macronutrients and fiber data were assessed using the software Dietpro Clínico 5.0. Six 24HRs were collected in total, and the mean of the week and weekend 24HRs was used for each of the three evaluation moments.

Title: Influence of the Sleep Pattern in Patients Submitted to Bariatric Surgery

NCT number: 03485352

Date: 03/04/2021

Statistical analysis

Data were analysed using SPSS software version 22.0 (SPSS, Inc., Chicago, IL, USA), and $p < 0.05$ was considered to be statistically significant. Data normality was tested by the Kolmogorov–Smirnov test.

The Student's t-test for independent samples or the Mann–Whitney test was performed to compare independent variables, according to the variable's distribution. Pearson's chi-square test was used to compare the proportion variables. The participants were categorized as follows: initially, the mean exposure to SJL of the three assessment periods was calculated. Subsequently, the median of this distribution was determined and used to categorize the participants into two groups: large exposure to SJL (mean exposure $>$ median) or small exposure to SJL (mean exposure \leq median).

Generalised estimating equations with gamma distribution and adjusted for possible confounding factors were used to examine the effect of follow-up time, SJL exposure level (large or small) and the interaction between these factors on the evolution of metabolic, food consumption and anthropometric parameters in the preoperative evaluation, and in the third and sixth months after the surgical intervention. Metabolic variables analyses were adjusted for sex, age, surgical technique, family income, use of sleep medications, physical activity, BMI, energy intake, type II diabetes mellitus and shift work. Anthropometric and food intake variables analyses were adjusted for all the same variables that were used in the adjustments of the metabolic analysis, except for BMI and energy intake, respectively.

Generalised Linear Models with gamma distribution and adjusted for confounding factors were used to verify the effect of exposure to SJL level (large or small) on the difference (delta) in anthropometric and metabolic parameters between the preoperative evaluation and the sixth month after surgery. Sequentially, Sidak's test was performed to verify the pairwise comparisons (higher and lower exposure to SJL) in the Generalised Estimating Equations and Generalised Linear Models analyses.

Multiple linear regression analysis adjusted for possible confounding factors (sex, age, family income, diagnosis of type II diabetes, surgical technique, shift work, use of sleep medication, physical activity and energy intake) was performed to evaluate the association between the mean SJL at the three assessment periods and the delta of the anthropometric and metabolic parameters, considering the period from the preoperative evaluation to the sixth month after surgery. The dependent variables (anthropometric and metabolic parameters) that violated the assumption of normality were transformed using the common log transformation.

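### The gamma GLM is fitted to a change score with no stated sign and no rule for zero or negative values, which the gamma distribution cannot take; the metabolic outcomes are the most exposed

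*SAP*

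**What the plan says.** The SAP's Statistical analysis section says of the Generalised Linear Models: "gamma distribution and adjusted for confounding factors were used to verify the effect of exposure to SJL level (large or small) on the difference (delta". It describes the outcome as the "difference (delta) in anthropometric and metabolic parameters between the preoperative evaluation and the sixth month after surgery". It then bases Sidak pairwise comparisons on this model as well as on the GEE.

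The metabolic outcomes are listed under Metabolic profile in the Protocol: "Serum levels of fasting glycaemia, fasting insulin, total cholesterol (TC), high density lipoprotein (HDL), low density lipoprotein (LDL), very low density lipoprotein (VLDL) and triglycerides". On timing, Follow-up evaluations says "Biochemical parameters were assessed at baseline and in the sixth month".

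Neither document states whether delta is baseline minus month 6 or the reverse. Neither says that delta is an absolute value or a ratio, or that a constant is added. Neither gives a rule for values at or below zero. The only absolute difference defined anywhere is the one used to compute social jetlag (SJL) itself. The link function is also not stated.

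The last SAP paragraph fits a multiple linear regression to the same deltas and says that dependent variables "that violated the assumption of normality were transformed using the common log transformation".

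**The concern.** The gamma density exists only above zero. Whichever sign is chosen, a patient whose marker is unchanged, or moves against the coded direction, has a delta that the stated model cannot use. Glycaemia, insulin and the five lipid measures can move either way in individual patients, and one sign need not suit all seven. HDL, for example, may move opposite to the others. That non-positive metabolic deltas occur is an inference, since the documents give no distribution of change.

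Weight, BMI and circumferences should be little affected if delta is coded as a decrease. If it is coded as month 6 minus baseline, nearly all of them would be negative. The missing sign therefore matters for both families of outcome.

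The analyst must exclude, shift, take absolute values or change the model. Excluding wrong-signed patients selects on the outcome, and taking absolute values counts a worsening as an improvement. Either can hide a real SJL contrast or create a false one, and a reader could not tell which route was taken or how many patients were analysed.

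A secondary, conditional point is that if the variables logged in the linear regression are the deltas, the common log fails at the same values. The SAP's parenthesis there may instead mean the raw parameters, which are positive, so no weight is put on this.

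**Working it through.** **Inputs from the documents.** The sample size is 116 (Protocol, Participants and ethics), in two groups split at the median of mean SJL, so about 58 each. There are seven metabolic outcomes measured at two visits.

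**The plan's own figure.** The only computed figure is N = 116, and it reproduces. With two groups, three measurements and f = 0.15, and assuming a correlation of 0.5 and sphericity (neither is stated), the noncentrality is 0.15² × 116 × 3 / (1 − 0.5) = 15.66 on 2 and 228 df. Power is 0.950. It is used below only as the number of patients.

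**Assumptions, none given in the documents.** Deltas are normal with SD 1 and mean k in the coded direction. The analysis is unadjusted, with 58 per group. Where a true difference is stated it is 0.5 SD, with group means k − 0.25 and k + 0.25. An SD of 1.3 in one group illustrates unequal spread.

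**Step 1: support.** The gamma log-density is minus infinity at 0 and at −1. A gamma GLM run on simulated deltas that included negative values returned an undefined log-likelihood.

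**Step 2: how many patients.** The share at or below zero is Φ(−k). The chance of at least one among 116 is 1 − (1 − Φ(−k))^116.

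| k | share ≤ 0 | expected of 116 | chance of at least one |
|---|---|---|---|
| 0.5 | 30.9% | 35.8 | >99.9% |
| 1 | 15.9% | 18.4 | >99.9% |
| 2 | 2.3% | 2.6 | 93% |
| 3 | 0.13% | 0.2 | 14.5% |

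With the opposite sign at k = 3, about 115.8 of 116 would be non-positive.

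**Step 3: what handling does to the group difference.** After exclusion, a group with mean μ and SD σ has mean μ + σφ(μ/σ)/Φ(μ/σ). At k = 1 with equal SDs, the group means 0.75 and 1.25 become 1.139 and 1.454, so 0.5 becomes 0.315. Absolute values use the folded-normal mean.

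| Scenario | k = 0.5 | k = 1 | k = 2 | k = 3 |
|---|---|---|---|---|
| True 0.5, equal SDs, exclusion | 0.24 | 0.31 | 0.44 | 0.49 |
| True 0.5, equal SDs, absolute value | 0.19 | 0.34 | 0.48 | 0.50 |
| True 0.5, SD 1.3 in higher-mean group, exclusion | 0.47 | 0.50 | 0.53 | 0.51 |
| True 0.5, SD 1.3 in lower-mean group, exclusion | 0.01 | 0.09 | 0.30 | 0.45 |
| True 0, SD 1 vs 1.3, exclusion | 0.23 | 0.21 | 0.11 | 0.03 |

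**Step 4: rejection rates at the 0.05 level.** These come from 10,000 simulated studies per cell, using a two-group gamma GLM with Pearson dispersion. Log and identity links agree within 1 point on power.

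| Scenario | k = 0.5 | k = 1 | k = 2 | k = 3 |
|---|---|---|---|---|
| True 0.5, Gaussian with robust SE, all patients | 76% | 76% | 76% | 77% |
| True 0.5, gamma after shift, all patients | 76% | 76% | 76% | 77% |
| True 0.5, gamma after exclusion | 35% | 49% | 71% | 76% |
| Equal means, SD 1 vs 1.3, gamma after exclusion | 26% | 21% | 9% | 5–6% |
| Equal means, SD 1 vs 1.3, Gaussian with robust SE | 5% | 5% | 5% | 5% |
| Identical distributions, gamma after exclusion | 5% | 5% | 5% | 6% |

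**Step 5: the shift.** Moving all deltas up by a constant keeps the power, but under a log link the estimated ratio depends on the constant. With means 0.25 and 0.75, adding 2 gives 2.75/2.25 = 1.22 and adding 3 gives 3.75/3.25 = 1.15, for the same data.

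**The case against.** **The harm is hypothetical.** No passage gives the mean, SD or sign of any delta. At k = 3 nothing of note happens, and if both groups share one delta distribution there is no bias. This stands as a limit on size. It does not touch the fact that the stated model is undefined for some possible data and that no rule is given.

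**The scenarios are generous.** The SD ratio of 1.3 is illustrative. At a ratio of 1.1, false rejection after exclusion is only about 5–8% across the range of k. At a true difference of 0.3 SD, power is about 36% on all patients against 16%, 22%, 33% and 36% after exclusion, so the absolute loss is roughly half of that at 0.5 SD. Skewed deltas were not examined. All of this is accepted: the spurious-difference figures show what can happen, not what is expected.

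**Other analyses cover the question.** Because biochemistry is measured only at baseline and month 6, the gamma GEE time-by-SJL term on positive levels addresses the same metabolic change, although its scale may differ. The linear regression also models delta, with continuous SJL, and is unaffected wherever delta is left untransformed. No passage names the delta GLM as primary. This confines the damage to the delta GLM and its Sidak comparisons, but that is still a reported analysis.

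**Replacing the model is a preference.** A shifted gamma loses no power, and an explicit rule would close the gap. That is partly right: a declared rule is the minimum. The Gaussian model is still preferable because it uses everyone and its contrast does not depend on an arbitrary constant.

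**Conclusion.** The concern holds. As written, the delta GLM cannot be applied to any patient with a zero or wrong-signed change, and the SAP leaves the handling of those patients open. That part is certain: it follows from the support of the gamma distribution and from the absence of any sign or rule in either document.

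The size is conditional on the assumptions listed in the calculation. If the average change is 0.5 to 1 SD, exclusion would affect about 36 to 18 of 116 patients and roughly halve a 0.5 SD contrast (0.24) or cut it by over a third (0.31). If SDs also differ, the bias can go either way. If the average change is 3 SD or more in the coded direction, as may be true of weight and BMI coded as a decrease, the problem is negligible.

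This should be corrected before the delta results are relied on. It does not undermine the GEE analyses.

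**What to change.** 1. Define delta for each outcome, including the order of subtraction.
2. Replace the gamma GLM on delta with a Gaussian identity-link model using the same covariates, with robust or bootstrap standard errors, on all patients with both measurements. The SJL contrast is then a difference in mean change, in the outcome's own units.
3. Do not log deltas. If relative change is wanted, model the log of the month-6 to baseline ratio and say that the estimand has changed.
4. Report the number analysed per outcome and SJL group.
5. The SAP is written in the past tense, so a handling choice may already have been made. If values were shifted, made absolute or excluded, disclose this with the constant used and the counts by group.

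The cost is a few sentences in the SAP and a re-run of the delta models on existing data.

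### The regression's log rule has no defined result for changes that are zero or run against the coding, and its normality check is aimed at the outcome, not the residuals

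*SAP*

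**What the plan says.** All of this is in the SAP's Statistical analysis section unless noted.

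- **Outcome.** The multiple linear regression relates mean social jetlag (SJL) over the three assessments to "the delta of the anthropometric and metabolic parameters, considering the period from the preoperative evaluation to the sixth month after surgery", adjusting for nine covariates that include sex, type II diabetes and surgical technique.
- **Rule.** The next sentence has as its subject "The dependent variables (anthropometric and metabolic parameters) that violated the assumption of normality"; it states that those "that violated the assumption of normality were transformed using the common log transformation".
- **Check.** The only one named is at the start of the section: "Data normality was tested by the Kolmogorov–Smirnov test". Residuals are not mentioned anywhere.
- **Definition of delta.** In the description of the generalised linear models it is the "difference (delta) in anthropometric and metabolic parameters between the preoperative evaluation and the sixth month after surgery". The direction of subtraction is not given.
- **Markers.** The protocol, under Metabolic profile, lists "Serum levels of fasting glycaemia, fasting insulin, total cholesterol (TC), high density lipoprotein (HDL), low density lipoprotein (LDL), very low density lipoprotein (VLDL) and triglycerides".

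Neither document gives a shift constant, a sign convention, a log-ratio definition or a fallback for changes at or below zero.

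**The concern.** There are two separate problems.

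The first is the remedy. A change score can be positive, zero or negative, but a log exists only for positive numbers. If the change is coded as month 6 minus baseline, the log is undefined for every patient whose value fell. If it is coded as a loss, the log is undefined for every patient whose value stayed the same or rose. The analyst must then omit those patients, add a constant or change signs, and the SAP chooses none of these. Omission would select patients on the outcome. An added constant would make the coefficient depend on an arbitrary number. Even where it exists, the log of a difference has no simple meaning on the marker's own scale.

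The second is the trigger. Linear regression assumes roughly normal errors; it assumes nothing about the marginal distribution of the outcome. If a covariate in the model, such as diabetes, splits patients into groups with very different changes, the outcome can look non-normal while the residuals are well behaved. The rule would then transform a variable that needs no transformation.

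**Working it through.** **The plan's own figure.** The only design number is the total of 116 (protocol, Participants and ethics). With f = 0.15, 2 groups, 3 measurements, and an assumed correlation of 0.5 and sphericity of 1:

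- λ = f²·N·m/(1−ρ) = 0.0225 × 116 × 3 / 0.5 = 15.66
- df = 2 and (116−2) × 2 = 228
- power = 0.9501

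The figure reproduces, so 116 is used below. It has no bearing on the log rule itself.

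**Step 1: how many changes have no log, for outcomes that the rule would pick up.** The rule acts on non-normal outcomes, so the example must be skewed. Assume baseline and month-6 values are log-normal with equal log-SD s and log-scale correlation ρ, and that the median month-6 value is r times the median baseline value. Code the change favourably, as a loss. Then

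P(change ≤ 0) = Φ(ln r / τ), with τ = s·√(2(1−ρ)).

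First row: τ = 0.45 × √1 = 0.45; ln 0.5 / 0.45 = −1.540; Φ = 0.0617; × 116 = 7.2 patients. The rejection rates come from 8,000 simulated samples of 116 per row, tested at 0.05.

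| s | ρ | r | Share without a log | Of 116 | Fails Lilliefors-corrected KS | Fails uncorrected KS |
|---|---|---|---|---|---|---|
| 0.45 | 0.5 | 0.50 | 6.2% | 7 | 82% | 26% |
| 0.5 | 0.5 | 0.55 | 11.6% | 13 | 85% | 31% |
| 0.5 | 0.5 | 0.65 | 19.5% | 23 | 76% | 22% |
| 0.6 | 0.5 | 0.80 | 35.5% | 41 | 83% | 30% |
| 0.6 | 0.55 | 0.85 | 38.8% | 45 | 83% | 28% |

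The values of s, ρ and r are assumptions, because the documents give no distributions. The smaller the typical fall, the more patients have no log.

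**Step 2: when the log is harmless.** For an outcome whose mean loss is 3 SD, a normal approximation gives Φ(−3) = 0.0013, or 0.2 of 116 patients at or below zero. A consistently large loss can therefore be logged if it is coded as positive.

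**Step 3: checking the outcome or the residuals.** Simulated samples of 116 (2,000 per setting) had normal errors, a skewed SJL variable, and one binary covariate with an assumed prevalence of 25%. Share rejecting normality at 0.05:

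| Covariate effect (residual SD) | Outcome, Lilliefors | Residuals, Lilliefors | Outcome, uncorrected KS |
|---|---|---|---|
| 0 | 4% | 4% | 0% |
| 1 | 5% | 3% | under 0.1% |
| 2 | 21% | 4% | 0.6% |
| 3 | 88% | 4% | 23% |
| 3.75 | 99.9% | 4% | 79% |

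A second set-up, with a diabetes effect of 1, 2 or 3 SD and a sex effect of half that size, gave 5%, 19% and 72% for the outcome with the Lilliefors correction. Residuals gave 3% to 5%, and the uncorrected test gave 0.05%, 0.9% and 11%. The SAP does not say which version of the test was used.

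**The case against.** The best defence is that the rule may not mean what it literally says. The SAP's parenthesis describes the dependent variables as the parameters, not their changes, so the parameters may have been logged before subtraction. That would be sound. But the sentence before it makes "the delta of the anthropometric and metabolic parameters" the outcome, and no difference of logs or ratio is mentioned. The ambiguity is genuine and needs an explicit statement.

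It can also be said that testing the outcome is often loose wording for checking residuals. That is possible, but the text attaches normality to the dependent variables and to the data.

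Several stronger readings are tempting and are not supported:

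- **That the log can never be used on these changes.** One-signed losses coded as positive can be logged, as Step 2 shows.
- **That 16%, 31% or 42% of patients (18, 36 or 49 of 116) have no log.** These shares follow from normal changes with means of 1, 0.5 and 0.2 SD. The rule leaves normal outcomes alone apart from false rejections, so they do not measure its effect.
- **That needless transformation is near certain.** This takes a covariate effect of about 3.75 residual SD and the Lilliefors correction. The documents support neither.
- **That patients were dropped.** Nothing in either document says so; a shift or a sign change is equally possible.

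The scope is also limited. The generalised estimating equations analyse parameter levels and do not use this log step.

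**Conclusion.** The point stands in a limited form. Followed as written, the rule has no defined result for changes that are zero or opposite to the coding. That much needs no numerical assumption. Its size does: under the log-normal assumptions above, roughly 7 to 45 of 116 patients are affected for a skewed metabolic marker. Such a marker fails the corrected check in about 76% to 85% of samples, and the uncorrected check in only about 22% to 31%.

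The misdirected check is the lesser problem. It matters for covariate effects of about 2 residual SD or more with the corrected test, and nearer 3 SD with the uncorrected one; at 1 SD or less it makes almost no difference. The rule should be changed, but it affects one association analysis and not the whole plan.

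**What to change.** Replace the transformation rule with the following:

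1. State the direction of subtraction, and fit the regression to the untransformed change with all patients who have both values.
2. Assess the residuals, mainly by plot. If they are skewed or heteroscedastic, use HC3 or bootstrap standard errors.
3. For strictly positive skewed markers such as insulin and triglycerides, log the baseline and month-6 values first and regress the difference of logs. This exists for every patient with two positive values, whichever way the marker moved. With common logs and a slope b, 10^b is the factor by which the month-6 to baseline ratio changes per unit of mean SJL; report that ratio. Name these markers in the SAP and do not let a test choose them.
4. If the parameters were in fact logged before subtraction, say so and give the ratio interpretation.

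The cost is a change of wording and a rerun of one analysis on existing data. The sample size of 116 is unaffected. The drawback is that some markers are reported as ratios and others as differences.
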